In theory, patients with Eustachian tube dysfunction as defined by negative pressure on tympanometry will have more resistance in the Eustachian tube. Thus, the pressure required to open should be higher than the pressure in patients with normal function. This relationship has never been evaluated. It would have an impact not only when considering CPAP as a treatment modality, but also when considering CPAP in post-operative patients undergoing otologic surgery. We hypothesize an inverse relationship between middle ear pressure and air pressure as delivered by CPAP required to create both subjective (“popping” the ears) and objective (tympanometric and otoscopic) increase in middle ear pressure. We will begin recruiting participants from clinic and the general population. Each individual participant will be assigned a participant ID. The participant will be brought to the exam room and fitted with a new CPAP mask. Photodocumentation of otoscopic examination will be obtained for baseline as well as tympanometric measurement. Starting at a set pressure, the patient will be given a set number of breaths. Then, the setting will be increased until a maximum tolerable pressure is reached (no higher than 20 cm H₂O). The participant will be asked to notify the examiner when he or she has a sensation of his ears “popping”, and that level will be documented. Photodocumentation and tympanometric measurement will be obtained. These will be used to plot correlation between opening pressure and both initial middle ear pressure as observed on tympanometry and otoscopic evaluations. The Sade classification scheme will be used to grade otoscopic findings. These findings will be analyzed using SPSS and tests include Spearman correlations, t-tests, and Wilcoxon Rank-Sum Test.

Background

1. Provide the scientific background, rationale and relevance of this project.

Eustachian tube dysfunction and chronic otitis media

Eustachian tube dysfunction is a poorly defined and understood clinical entity. While it is agreed upon that it is the primary etiology of chronic otitis media, particularly in adults, the exact physiology has been elusive. While many different theories have been proposed with evidence presented in addition, *Cummings* (Flint, *et al.*) describes two key physiological changes, whether it be mechanical obstruction (e.g., adenoid hypertrophy) or functional (normal anatomy with poor function). The former is likely more common in children with the latter best described in patients with cleft palate. Purely anatomical comparisons have not provided a definite etiology for why some individuals have significantly greater dysfunction.

In describing the clinical entity of Eustachian tube dysfunction, the literature varies between symptom descriptions, objective findings, and clinical outcomes (ie, need for surgery, etc.). Even when using objective findings, there is disagreement as to what degree of negative pressure on tympanometry constitutes Eustachian tube dysfunction. Attempts to measure function have been unsuccessful. A recent review by Norman, *et al.* found such significant variation in how ETD was defined in the literature that it was felt that no reasonable conclusions could be drawn regarding specific, consistent diagnostic criteria. While multiple symptom score indices have been proposed, including the Eustachian tube dysfunction questionnaire (ETDQ-7, Figure 1), they have not reached widespread use.

Figure 1. The Seven Item Eustachian Tube Dysfunction Questionnaire (ETDQ-7).

Over the past 1 month, how much has each of the following been a problem for you?	Severe Problem						
	No Problem	Moderate Problem					
1. Pressure in the ears?	1	2	3	4	5	6	7
2. Pain in the ears?	1	2	3	4	5	6	7
3. A feeling that your ears are clogged or “under water”?	1	2	3	4	5	6	7
4. Ear symptoms when you have a cold or sinusitis?	1	2	3	4	5	6	7
5. Crackling or popping sounds in the ears?	1	2	3	4	5	6	7
6. Ringing in the ears?	1	2	3	4	5	6	7
7. A feeling that your hearing is muffled?	1	2	3	4	5	6	7

Treatment of ETD has also been elusive. While many methods have been proposed, including but not limited to devices such as the Otovent (Kestrel Medical, United Kingdom), surgical interventions such as balloon dilation, myringotomy with ventilation tube placement, laser coagulation, and others, none has provided sufficient data to prove a long-term benefit of the stated intervention. The value of preventing progression of chronic otitis media and its sequelae – including cholesteatoma, hearing loss, severe infections, and need for repeated surgical interventions – is unquestioned.

Continuous positive air pressure therapy

Continuous positive air pressure therapy (CPAP) is a highly successful treatment of an increasingly common problem – obstructive sleep apnea (OSA). Patients using CPAP for OSA have been evaluated in regard to middle ear function. Common otologic complaints related to CPAP include aural fullness and the development of serous otitis media. On the whole, CPAP use is quite safe for the middle ear, although rare case reports have suggested association with negative side effects including a single report of perilymph fistula formation. The most likely mechanism by which the ears are affected by CPAP is that air is forced into the Eustachian tube. Multiple studies have found higher middle ear pressures with CPAP use, although in patients without ETD, the middle ear pressure is likely to revert to a normal pressure. The impact of CPAP on the middle ear still has significant room for investigation.

Hypothesis to be Tested

There is a specific CPAP pressure at which individuals’ Eustachian tubes will allow air to be transmitted to middle ear. We will be able to correlate this to initial middle ear pressure.

Primary outcome measure: CPAP pressure required for middle ear insufflation.

Secondary outcome measures:

- Change in middle ear pressure with CPAP use
- Otoscopic findings
- Patient symptom survey (ETDQ-7)

Study Design: Biomedical

1. Will controls be used? No
2. What is the study design? Cohort study
3. Does the study involve a placebo? No

Human Participants

Ages: 18-99

Sex: M or F

Race: Any

Subjects- see below

1. **Provide target # of subjects (at all sites) needed to complete protocol.** 29
2. **Describe expected rate of screen failure/ dropouts/withdrawals from all sites.** 5%
3. **How many subjects will be enrolled at all sites?** 31
4. **How many subjects will sign a consent form under this UVa protocol?** 31
5. **Provide an estimated time line for the study.**

After IRB approval, we anticipate completion of enrollment and study completion within 2 months. Data analysis will be concluded within 6 months of study initiation. No follow up is required.

Inclusion/Exclusion Criteria

1. List the criteria for inclusion

- Age \geq 18
- No use of CPAP within past 30 days
- Individuals presenting to the UVA otolaryngology clinic who are otherwise healthy

2. List the criteria for exclusion

- Pre-existing cardiopulmonary disease that presents a risk with CPAP use
- Inability to tolerate CPAP
- Recent otologic surgery

3. List any restrictions on use of other drugs or treatments. None

Statistical Considerations

1. Is stratification/randomization involved?

As there will be no comparison group, there will not be stratification or randomization. Any grouping will be performed in the data analysis portion based on data acquired within the study.

2. What are the statistical considerations for the protocol?

Primary endpoint:

- CPAP pressure at which a significant change in middle ear pressure occurs

Secondary endpoints:

- Tympanometry
- Otoscopy
- ETDQ-7

3. Provide a justification for the sample size used in this protocol.

We anticipate accruing 5-10 participants per week. The accrual goal will be 32, with an interim analysis at 16. We anticipate a very low dropout rate, but will account for a 5% rate. Based on calculations assuming a -0.500 correlation between “opening pressure” (CPAP pressure) and starting middle ear pressure, 29 participants are needed to show statistically significant differences. There is no required follow up, so this provides minimal drop-out risk.

4. What is your plan for primary variable analysis?

We will perform Spearman correlation calculations to estimate the relationship of CPAP pressure at which the ears “pop” to the initial and final tympanometric pressure as well as the change in tympanometric pressure.

5. What is your plan for secondary variable analysis?

We will use t-tests and/or ANOVA to assess the relationship of the above pressures to ETDQ-7 responses as well as using ROC curve analyses to determine if there is a true tympanometric pressure cut point to define ETD.

6. Have you been working with a statistician in designing this protocol? No

7. Will data from multiple sites be combined during analysis? No

Biomedical Research

1. What will be done in this protocol?

- Each individual participant will be assigned a participant ID.
- The participant will be brought to the exam room and fitted with a new CPAP mask.
- Photo-documentation of otoscopic examination will be obtained for baseline as well as tympanometric measurement.
- Starting at a set pressure, the patient will be given a set number of breaths. Then, the setting will be increased until the maximum tolerable pressure or a maximum pressure of 20 cm H₂O has been reached.
- The patient will be asked to notify the examiner when he or she has a sensation of his ears “popping”, and that level will be documented.
- Photo-documentation and tympanometric measurement will be obtained.

2. List the procedures, in bullet form, that will be done for RESEARCH PURPOSES as stipulated in this protocol.

- Tympanometry
- Otoscopy
- Short term use of CPAP (10 minutes)
- ETDQ-7 for our research purposes.

3. Will you be using data/specimens in this study that were collected previously, with the use of a research consent form, from another research study? No

4. Will any of the procedures listed in item # 2 have the potential to identify an incidental finding? This includes ALL procedures, assessments and evaluations that are being done for RESEARCH PURPOSES that may or may not be considered investigational. yes

This examination(s) utilizes non-standard/investigational, technique, equipment, etc. It is impossible to determine the significance of such results, therefore abnormalities will not be shared with the subject because the meaning of the exam is not yet proven and is of unknown clinical benefit.

5. Do any of the procedures listed above, under question # 2, utilize any imaging procedures for RESEARCH PURPOSES? No

6. Will you be using viable embryos? No

7. Will you be using embryonic stem cells? No

8. Are any aspects of the study kept secret from the participants? No

9. Is any deception used in the study? No

10. If this protocol involves study treatment, explain how a subject will be transitioned from study treatment when they have completed their participation in the study. NA

11. Will your study involve measures (C-SSRS/BID/SCID etc.) used to assess for depression and/or suicidality for research purposes? No

Taping/Photography

1. Will participants be recorded on audiotape? No

2. Will participants be photographed or recorded on videotape? Yes

▶ IF YES, answer the following questions.

2a. Will their faces be shown? No

2b. What steps will be taken to protect the privacy of the subjects?

The device used to take the photographs (iPhone) will be secured per UVA protocol and only used for research purposes. The images will only be tied to a participant ID. The images will only be of the ear drum and as such will not allow for identification if seen.

2c. What data will be captured from the photo or videotape that could not be obtained in other ways? Image of the tympanic membrane (ear drum). This cannot otherwise be reviewed in a blinded fashion.

2d. How is this data critical to this research?

This provides an additional clinical measurement that allows for analysis of patients.

2e. When will data from the tapes be transcribed?

Within one month of obtaining them they will be transferred to a secure file and deleted from the portable device.

2f. When will the tapes be destroyed?At the conclusion of the study.

2g. Will participants be photographed, recorded or videotaped without their knowledge?
No

3. If a subject withdraws from the study how will you withdraw them from the audiotape, videotape or photograph? Delete the files.

Data and Safety Monitoring Plan

1. Definition:

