5.4 How often will aggregate review occur?

For additional information on aggregate review see:

www.virginia.edu/vpr/irb/hsr/continuations.html#aggreview

NA- PI is not the overall person overseeing the safety data for this study.

Per Enrollment/Events

Annually

5.5. How often will a report, regarding the outcome of the review by the DSMB/DSMC, be sent to the UVa PI? n/a

5.6. How will a report of the information discussed in question 5.4 OR 5.5 be submitted to the IRB?

Part of IRB-HSR continuation status form

Risk/ Benefit Analysis

1. What are the potential benefits for the participant as well as benefits which may accrue to society in general, as a result of this study?

We do not anticipate any direct benefits to the patient in this study. We anticipate a benefit to society in that we will have a better understanding of the amount of CPAP pressure required to affect the middle ear. This may allow for use as treatment (for patients with ETD) and/or for advisory data in post-operative patients after ear surgery.

2. Do the anticipated benefits justify asking subjects to undertake the risks?

The risks of this procedure are seen as very low. The subjects will be screened for any comorbid cardiopulmonary disease that may increase the risk of adverse events with CPAP use.

Bibliography

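### The primary outcome is a CPAP pressure level, but no planned analysis estimates that level or its uncertainty

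*Combined protocol and SAP*

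**What the plan says.** Under Hypothesis to be Tested there are two statements. The first is that a particular CPAP pressure exists at which air gets through; the second is that this pressure can be related to baseline: "Eustachian tubes will allow air to be transmitted to middle ear. We will be able to correlate this to initial middle ear pressure". The outcome line that follows reads "Primary outcome measure: CPAP pressure required for middle ear insufflation". Statistical Considerations, item 2, gives the primary endpoint as "CPAP pressure at which a significant change in middle ear pressure occurs". Both are levels in cm H2O.

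Item 4, the primary analysis, reads "We will perform Spearman correlation calculations to estimate the relationship of CPAP pressure" at popping to initial tympanometric pressure, final tympanometric pressure and the change between them. Item 5 reads "We will use t-tests and/or ANOVA to assess the relationship of the above pressures to ETDQ-7 responses as well as using ROC curve analyses", the ROC being aimed at a tympanometric definition of ETD. The protocol summary also names the Wilcoxon rank-sum test. Item 3 bases the 29 participants on an assumed correlation of -0.500.

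The Risk/Benefit Analysis, item 1, describes the expected gain as "a better understanding of the amount of CPAP pressure required to affect the middle ear", with possible use in treating ETD and in advising patients after ear surgery.

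Biomedical Research, item 1, has the popping level documented for each participant. The ramp ends at the highest level the participant tolerates or at 20 cm H2O.

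**The concern.** The declared primary outcome and the stated benefit are about how much pressure is needed. No planned analysis returns a mean, a median, a proportion opened by a given pressure, or a confidence interval for any of these. The study could be analysed exactly as written, report a correlation coefficient, and leave its primary outcome without an estimate.

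The gap would probably be filled at the reporting stage with a mean or median of the documented popping levels. That summary leaves out anyone whose ears never popped, and the plan does not say how such participants are handled. Leaving them out makes ears appear to open at lower pressures than they do.

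**Working it through.** **1. The plan's own figure.** Inputs from item 3: correlation -0.500, N = 29. Alpha, sidedness and power are not stated; I assume two-sided 0.05 and 80%. By Fisher's z,

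n = ((1.960 + 0.842) / atanh(0.5))² + 3 = (2.802 / 0.5493)² + 3 = 29.01.

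The 29 reproduces. With 5% dropout, 29 / 0.95 = 30.5, which rounds up to the 31 enrolled under Human Participants. The sample size therefore serves the correlation; nothing in it concerns the precision of a pressure.

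**2. What the primary analysis returns.** If the observed correlation is -0.50 with n = 29, the approximate 95% CI is tanh(-0.5493 ± 1.96/√26), or -0.73 to -0.16. That is unit-free. A rank correlation is also unchanged by shifting or rescaling the pressures. In one simulated set of 29 participants, rescaling the same values to a mean opening pressure of 8.1 or of 14.2 cm H2O gave the identical Spearman coefficient (-0.226). The coefficient carries no information about the level.

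**3. What the other analyses return.** T-tests and ANOVA compare pressures across ETDQ-7 responses. The Wilcoxon rank-sum test compares groups. The ROC looks for a tympanometric cut point, not a CPAP one. None estimates the overall opening pressure.

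**4. Bias of the simple summary.** Let q be the proportion not opened when the ramp ends. If their opening pressures all lie above those observed, the median of the openers is the (1 - q)/2 quantile of the full distribution. Under a normal distribution it understates the true median by SD × |z((1 - q)/2)|. The documents give neither q nor the SD, so both are assumed.

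| q | quantile | absolute z | SD 4 | SD 6 |
|---|---|---|---|---|
| 10% | 45th | 0.1257 | 0.5 | 0.8 |
| 40% | 30th | 0.5244 | 2.1 | 3.1 |

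(Shortfall in cm H2O; for example, 0.5244 × 6 = 3.146.) The formula ignores tolerance stops at levels where others have yet to open, so it is approximate.

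The mean behaves in the same way. With an assumed mean of 12 and SD 4, 2% do not open by 20 cm H2O and openers average 11.8. With mean 16 and SD 5, 21% do not open and openers average 14.2. With mean 18 and SD 4, 31% do not open and openers average 16.0. If nearly everyone opens, the bias is negligible.

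**5. Precision available at 29 evaluable.** Exact binomial 95% CIs for the proportion opened by a given pressure are:

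- 14/29: 29% to 67%
- 20/29: 49% to 85%
- 26/29: 73% to 98%

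Without censoring, the interval for the median runs from the 9th to the 21st ordered value (coverage 97.6%). Censoring below 20 cm H2O would widen these somewhat.

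**The case against.** The best defence is that the plan is coherent around its central hypothesis. The summary predicts an inverse relationship, item 3 sizes the study for it, and item 4 tests it. On this view the primary outcome line only names the variable measured, and the sentence about a specific pressure refers to each individual's own threshold, which is observed directly. The summary's remark about impact, "but also when considering CPAP in post-operative patients undergoing otologic surgery", is attached to that relationship and not to a population distribution. The values would in any case be visible in the planned plots.

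Much of this stands. A reader might infer that correlations are the only analyses planned; that is true of item 4, but other methods are named. A reader might infer that the study cannot deliver an opening pressure; the documents do not support that, because the popping level is documented for each participant and only the analysis is missing. Nor do they support saying that every stated use depends on the distribution, since the summary ties its uses to the relationship. Finally, no biased mean or median is actually planned, so the bias figures describe a likely default and not an error in the text.

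What the defence does not meet is the Risk/Benefit Analysis, which links the same uses to the amount of pressure required, and two separate statements of the primary quantity as a level. A scatter plot of recorded pops shows neither the non-openers nor any uncertainty.

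**Conclusion.** The point holds as a gap in the analysis plan. It is not a fault in the design, the sample size or the correlation test. The primary outcome and endpoint are a pressure level, and no planned method estimates that level with its uncertainty. This conclusion rests on the text alone.

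The size of the bias in a summary of openers only is not known from the documents. The range of 0.5 to 3.1 cm H2O for the median depends wholly on the assumed 10% to 40% not opening, SD of 4 to 6 cm H2O and normality. Its direction, too low, needs only that some participants do not open before the ramp ends and that their opening pressures would have been higher than the typical opener's.

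**What to change.** Add to Statistical Considerations, item 4, as the estimate for the primary outcome:

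- **Estimate.** The cumulative proportion of participants opened by each CPAP step up to 20 cm H2O, by the product-limit method over pressure, with 95% CIs, and the median opening pressure with its CI if reached.
- **Event.** Define opening as the reported pop. It is the only event documented by level; tympanometry is listed at baseline and once afterwards. Reconcile this with the primary endpoint, which refers to a change in middle ear pressure.
- **Non-openers.** Record the last level reached by anyone who never pops, and right-censor them there. The procedures do not now say this level is recorded.
- **Sensitivity analysis.** Count participants who stop for intolerance as not opened by 20 cm H2O, keeping them in the denominator at every step. The product-limit method assumes that stopping is unrelated to the opening pressure, and ear discomfort could make that untrue.
- **Correlation.** Keep Spearman as the test of the inverse relationship.

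The cost is one extra recorded field, one table or figure and a few lines of protocol text. Neither N nor the pressure procedure changes. The drawback is that the intervals will look wide at this sample size.

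### The named primary endpoint (CPAP level of a significant middle ear pressure change) cannot be located from two tympanograms. The planned analysis uses the self-reported pop level, which is not named as the endpoint and has no value for participants who never pop.

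*Combined protocol and SAP*

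**What the plan says.** The combined protocol and SAP describes the primary quantity in several ways.

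- **Statistical Considerations, item 2** gives the primary endpoint as the "CPAP pressure at which a significant change in middle ear pressure occurs".
- **Hypothesis to be Tested** gives "Primary outcome measure: CPAP pressure required for middle ear insufflation". The hypothesis concerns a pressure at which the "Eustachian tubes will allow air to be transmitted to middle ear". The same section makes "Change in middle ear pressure with CPAP use" a secondary outcome.
- **Statistical Considerations, item 4**, the primary variable analysis, begins "We will perform Spearman correlation calculations to estimate the relationship of CPAP pressure at which the ears" pop. It relates that level to the initial tympanometric pressure, the final one and the change between them.
- **Statistical Considerations, item 3** sizes the study at 29 for a correlation of -0.500 between opening pressure and starting middle ear pressure.
- **The opening summary** says of the recorded pop level and measurements: "These will be used to plot correlation between opening pressure and both initial middle ear pressure as observed on tympanometry and otoscopic evaluations". Its hypothesis separates a subjective response (popping) from an objective one (tympanometry and otoscopy).

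Biomedical Research item 1 lists a baseline tympanogram, a stepped increase in CPAP ending at individual tolerance or at 20 cm H₂O, and then one further tympanogram. For the CPAP level it says "The patient will be asked to notify the examiner when he or she has a sensation of his ears" popping, and that this level is documented. No other CPAP level is listed for documentation. Item 7 of the appendix on unapproved device use lets a participant stop at once for any discomfort.

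**The concern.** Two things are at stake.

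First, the report could not give the endpoint that the protocol names. It would give a correlation with a sensation, and a reader could take that for measured insufflation. The summary and the Risk/Benefit Analysis say the results may inform CPAP as treatment and advice after ear surgery, so the difference matters.

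Second, a participant who never pops has no value for the primary analysis. There are two kinds: those who reach the cap, whose opening level lies above it, and those who stop earlier, whose opening level may be ordinary. Under the study's own hypothesis the most negative ears need the highest pressures, so losing participants at the cap is not random. The session is a single encounter without follow-up, so the highest level reached and the reason for stopping may not be recoverable later if they are not recorded at the time.

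**Working it through.** **1. The plan's own figure.** Input: correlation -0.500 (item 3). Two-sided 0.05 and 80% power are assumed, because the plan states neither.

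n = ((1.95996 + 0.84162) / atanh(0.5))² + 3 = (2.80158 / 0.54931)² + 3 = 29.01.

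This matches the stated 29. With 5% loss, 29 / 0.95 = 30.5, hence the 31 to be enrolled. The arithmetic is not at fault.

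**2. What the measurements can locate.**

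| If the second tympanogram is taken | It shows | It does not show |
|---|---|---|
| at the pop | that pressure had or had not changed by that level | the level at which it changed |
| at the end of the ramp | change over the whole ramp | the level at which it changed |

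Item 4 calls the second reading final, and the procedures list it after the ramp. That points to the end of the ramp but does not settle it. Under either reading there is one post-baseline value and no numeric threshold, so the endpoint in item 2 cannot be derived.

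**3. Cost of having no rule for no-pop participants.** The documents give no no-pop rate, so 10%, 20% and 30% are assumed. Simulation: bivariate normal, r = -0.5, n = 29, two-sided Spearman test at 0.05, 10,000 trials per cell, tolerance SD equal to that of the opening level. Complete-data power is about 75%. Opening levels are treated as continuous; ties from CPAP steps are not modelled.

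| Scenario and rule | 10% | 20% | 30% |
|---|---|---|---|
| Common cap, no-pop dropped | 57% | 43% | 34% |
| Common cap, no-pop ranked on top | 75% | 74% | 73% |
| Half cap, half early stop, tolerance independent of baseline: all dropped | 60% | 48% | 37% |
| Same: cap-reachers on top, early stoppers out | 70% | 68% | 64% |
| Half and half, tolerance correlated 0.5 with baseline: cap-reachers on top, early stoppers out | 65% | 56% | 50% |

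At a common cap the rule moves power by 75 - 57 = 18, 74 - 43 = 31 and 73 - 34 = 39 points. Fewer participants is only part of it. In a separate run of 6,000 trials per cell, the mean Spearman coefficient after dropping also shrank, from -0.47 with complete data to -0.41, -0.37 and -0.35, because the highest opening levels are cut off.

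**4. Bias from early stoppers.** Here there is no true correlation, and tolerance is assumed to correlate 0.5 with baseline ear pressure. Two-sided error (nominal 5%):

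| Scenario and rule | 10% | 20% | 30% |
|---|---|---|---|
| All no-pop stop early: ranked on top | 6.0% | 8.1% | 11.7% |
| All no-pop stop early: left out | 6.2% | 7.7% | 9.5% |
| Half cap, half early: all on top | 5.3% | 5.9% | 7.0% |
| Half cap, half early: only cap-reachers on top, early stoppers out | 5.8% | 6.6% | 7.4% |

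The two rules err in opposite directions. With this sign, when all stop early, ranking on top gives false support for the inverse hypothesis in 4.3%, 7.3% and 11.2% of trials, against 2.5% nominal; leaving out gives 1.0%, 0.7% and 0.7%. Reversing the sign of the tolerance correlation swaps the directions. If tolerance is unrelated to baseline, every rule holds its level (4.7% to 5.5%).

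**The case against.** The strongest defence is that the pop level is plainly the opening pressure of the summary and of item 3, and that item 4 states it under the primary variable analysis. Most of this stands. A reader might infer that the plan analyses a hidden or switched variable; the documents do not support that, because the pop level is pre-specified in the open. Item 4 also relates it to the measured pressure change, which gives some check of the sensation against tympanometry. What remains is that no section names the pop level as the endpoint or equates a pop with insufflation, and the summary itself treats the two responses as different.

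A second defence is that inability to tolerate CPAP is an exclusion and that 5% is allowed for screen failure, dropout and withdrawal. The exclusion overlaps with early stopping and may remove some of that group. It does not clearly cover someone who tolerates part of the ramp, since the procedures treat reaching tolerance as an ordinary end. Neither provision covers a participant who completes the ramp to the cap without a pop.

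Third, the no-pop rates, the even split, the tolerance SD and the 0.5 correlation are all assumptions. That stands. The figures show how much depends on the rule, not what will happen in this study.

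**Conclusion.** The concern holds. As written, the named primary endpoint cannot be reported from the listed measurements, and the variable that will be analysed has no value for foreseeable participants. Aligning the two and stating a no-pop rule are necessary. The timing of the final tympanogram is secondary.

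At a common cap, dropping rather than ranking no-pop participants costs about 18, 31 or 39 points of power at assumed rates of 10%, 20% or 30%. With early stoppers mixed in, ranking only the cap-reachers still helps, but power is about 70%, 68% and 64%, or 65%, 56% and 50% if tolerance correlates 0.5 with baseline.

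Three stronger readings are not supported:

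- **That no-pop participants will be dropped.** The plan does not say so; it gives no rule.
- **That leaving early stoppers out is the safe choice**, because it rarely gives false support with the sign assumed here. Its two-sided error in that scenario is 6.2% to 9.5%, and the direction turns if the sign does.
- **That 29 is the wrong sample size.** It reproduces.

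**What to change.** 1. **Make endpoint and analysis agree**, in Hypothesis to be Tested and Statistical Considerations item 2. There are two options, and the choice is the investigator's.
   - Name the CPAP level at first reported pop as primary, limit the primary conclusion to felt opening, and keep tympanometric change secondary, as the outcome list already has it. This needs no new procedure, but objective insufflation is then no longer the primary claim.
   - Keep the objective endpoint, add tympanograms that locate the level, and state the numeric change that counts. This has to fit into procedures that Appendix: Recruitment item 7 puts at under 15 minutes.
2. **Pre-state a no-pop rule** in item 4 for the pop-level analysis. Rank participants who reach the protocol maximum without a pop, tied, above all observed pop levels. Report how many stopped earlier without a pop, run the Spearman analysis both leaving them out and ranking them on top, and report both results and any disagreement. State how the intolerance exclusion applies to these participants.
3. **Record** on the case report form the highest level reached and why the ramp ended.
4. **Reconcile** the summary, item 4 and Biomedical Research item 1 on whether the final tympanogram is taken at the pop or at the end of the ramp.

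With the first option the cost is wording, one form entry and one extra run, with no added visit, device or participant.
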